8.5.2. Study Stopping Criteria

The following study stopping criteria will be used during the study:

- The study will be stopped if two or more subjects develop the same CTCAE Grade 3 or if one subject develops a CTCAE Grade 4 of the following:
 - Injection site reactions
 - Opportunistic infections (i.e. tuberculosis)
 - Hypersensitivity reactions (e.g. allergic reactions, anaphylaxis or cytokine release syndrome)
 - Malignancy

- Decreased white blood cell count
 - Decrease neutrophil count
 - Decreased platelets
- The study will be stopped if two individual subjects develop any of the following liver toxicities:
 - ALT or AST >8x ULN
 - ALT or AST >5x ULN for more than consecutive 2 weeks or
 - ALT or AST >3x ULN with the appearance of fatigue, nausea, vomiting, right upper quadrant pain or tenderness, fever, rash and or eosinophilia (>5%).
- The study will be stopped if one subject meeting Hy's Law is detected (i.e. ALT or AST >3x ULN and total bilirubin >2x ULN and no other reason can be found to explain the combination of increased AT and TBL, such as viral hepatitis A, B, or C; preexisting or acute liver disease; or another drug capable of causing the observed injury).
- Individual reports of exacerbations of Crohn's disease CTCAE Grade 3 or greater, such as:
 - Colonic or ileal hemorrhage
 - Colonic, ileal or small intestine obstruction
 - Colonic, ileal or small intestine perforation
 - Colonic, ileal or small intestine stenosis

will be reviewed by the DMC at the first available date after report to determine if modifying the study or stopping the study is recommended.

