8.3. Safety Data Review

Each investigator will review all available safety data collected at their site on a weekly basis, and communicate any safety concerns to the sponsor medical monitor. The sponsor medical monitor will review all relevant safety findings with the coordinating principal investigator and DMC as needed.

Special attention will be paid to adverse drug reactions observed in the MDGN-002 preclinical study as well as other common adverse reactions seen with other biologic treatments which include:

MDGN-002 preclinical observation:

- Injection site reactions

Adverse reactions observed with other biologic treatments:

- Potential for increased infection including opportunistic infections (such as tuberculosis)
- Hypersensitivity reactions (including anaphylaxis)
- Immunogenicity
- Malignancy
- Impaired immunization
- CD exacerbation

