8.4. Data Monitoring Committee

An external, independent Data Monitoring Committee (DMC) comprising physicians, scientists and a biostatistician will review the study data at a meeting after all subjects in the first cohort have been enrolled and reached Visit 4 (Day 14 ± 3 days), and after completion of the second cohort. Additionally, ad hoc meetings to assess individual exacerbations of CD or UC meeting Common Terminology Criteria for Adverse Events (CTCAE) Grade 3 or greater as defined in [Section 8.5](#) may be held. The DMC's role is to protect the interests of the subjects in the study and those still to be entered in the study by reviewing information such as safety, tolerability, pharmacokinetic and efficacy data. The DMC's meeting schedule may be adjusted based on recommendations made by the DMC, the amount of incremental safety data, and other practical considerations. The data provided to the DMC may not be monitored and will not be considered "clean" until the database is locked at the completion of the study.

Possible outcomes of the DMC review can include one of the following recommendations:

- Study can continue
- Study can continue with modifications
- Study is to be terminated

Data Monitoring Committee recommendation will be documented in meeting minutes which will include, at a minimum:

- List of meeting participants
- Summary of data considered during the meeting
- Summary of the DMC recommendation regarding further dose cohorts, including any concerns raised

The sponsor is responsible for the decision to continue, modify or terminate the study. A copy of the DMC meeting recommendation and sponsor decision will be sent to the study sites upon completion and prior to administration of the next subject dose in the second cohort.

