8.5. Individual Subject and Study Stopping Criteria

8.5.1. Individual Subject Stopping Criteria

The following individual subject stopping criteria will be used during the study and will be assessed starting post-dose at Visit 2:

- A subject develops a CTCAE Grade 3 or higher of the following:
 - Injection site reactions
 - Opportunistic infections (i.e. tuberculosis)
 - Hypersensitivity reactions (e.g. allergic reactions, anaphylaxis or cytokine release syndrome)
 - Malignancy
 - Decreased white blood cell count
 - Decrease neutrophil count
 - Decreased platelets
 - Colonic or ileal hemorrhage
 - Colonic, ileal or small intestine obstruction
 - Colonic, ileal or small intestine perforation
 - Colonic, ileal or small intestine stenosis
- A subject will also be stopped if liver enzymes are:
 - ALT or AST >8x ULN
 - ALT or AST >5x ULN for more than 2 consecutive weeks or
 - A single subject ALT or AST >3x ULN with the appearance of fatigue, nausea, vomiting, right upper quadrant pain or tenderness, fever, rash and or eosinophilia (>5%).

Note: subjects who exhibit ALT or AST >3x ULN without appearance of any of the above symptoms must have repeat testing within 48-72 hours to confirm abnormality and determine direction (increase or decrease) from the original value.

- A subject will be stopped if Hy's Law is detected (i.e. ALT or AST >3x ULN and total bilirubin >2x ULN and no other reason can be found to explain the combination of increased AT and TBL, such as viral hepatitis A, B, or C; preexisting or acute liver disease; or another drug capable of causing the observed injury).

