12.3.1.6.3. Severity of Adverse Events

The severity of AEs must be recorded during the course of the event, including the start and stop dates for each change in severity. An event that changes in severity should be captured as a new event. Worsening of pre-treatment events after initiation of the investigational product must be recorded as new AEs. For example, if the subject experiences mild, intermittent headaches prior to dosing with investigational product and the headache intensity increases to moderate after the

first dose of investigational product, a new AE of moderate intermittent headaches is to be recorded in the source documents and eCRF.

The medical assessment of clinical severity of an AE will be determined using the definitions outlined in Common Terminology Criteria for Adverse Events (CTCAE), Version 4.0 (Published May 28, 2009 with Version 4.0.3 on June 14, 2010 by the US Department of Health and Human Services, National Institutes of Health, National Cancer Institute):

Grade 1	Mild; asymptomatic or mild symptoms; or clinical or diagnostic observations only; or intervention not indicated
Grade 2	Moderate; or minimal, local or non-invasive intervention indicated; or limiting age-appropriate instrumental activities of daily living (ADL)
Grade 3	Severe or medically significant but not immediately life-threatening; or hospitalization or prolongation of hospitalization indicated; or disabling; or limiting self-care ADL.
Grade 4	Life-threatening consequences; or urgent intervention indicated.
Grade 5	Death related to AE

It is important to distinguish between severe AEs and SAEs. Severity is a classification of intensity whereas an SAE is an AE that meets serious criteria as described in [Section 12.3.1.6.6.2](#).

Please refer to the above-referenced CTCAE document for full description of CTCAE terms and instrumental and self-care ADLs.

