NOTE: Medical and scientific judgment should be exercised in deciding whether it is appropriate to consider other situations serious, such as important medical events that may not be immediately life-threatening or result in death or hospitalization but may jeopardize the subject or may require intervention to prevent one of the other outcomes listed in the definition above. Examples of such events are intensive treatment in an emergency room or at home for allergic bronchospasm, blood dyscrasias or convulsions that do not result in hospitalization, or development of drug dependency or drug abuse.

12.3.1.6.6.3. Serious Adverse Event Collection Time Frames

All SAEs, regardless of the relationship to study, are collected from the time the subject signs the informed consent until the subject's last visit (office or telephone contact). The investigator or designee must report all SAEs promptly to the CRO and Aevi Genomic Medicine medical monitor within 24 hours of first becoming aware of the event.

Any SAE(s), regardless of relationship to IP, discovered by the investigator at any interval after the study has completed must be reported to the CRO and Aevi Genomic Medicine medical monitor within 24 hours of the first awareness of the event.

12.3.1.6.6.4. Serious Adverse Event Onset and Resolution Dates

The onset date of the SAE is defined as the date the event meets serious criteria (see [Section 12.3.1.6.6.2](#)). The resolution date is the date the event no longer meets serious criteria, the date symptoms resolve or the event is considered chronic. In the case of hospitalization, the hospital admission and discharge dates are considered respectively, the onset and resolution dates of the SAE.

Any signs or symptoms experienced by the subject after signing the informed consent form, or leading up to the onset date of the SAE or following the resolution date of the SAE must be recorded as AEs.

12.3.1.6.6.5. Fatal Outcome

An outcome of “fatal” should only be selected when the AE results in death. If more than 1 AE is possibly related to the subject’s death, “fatal” outcome should be indicated for each such AE.

Any AE that results in the subject’s death must have “fatal” checked as an outcome with the date of death recorded as the resolution date. Adverse events resulting in death must be reported within 24 hours as SAEs, if not already reported as such.

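### The one-subject study stopping rule names Grade 4 but not Grade 5, so a fatal listed event with no Grade 4 phase does not literally stop the study

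*Protocol*

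**What the plan says.** The first bullet of Protocol 8.5.2 is an automatic stop with two limbs, both applying to the same seven event types: injection site reactions, opportunistic infections, hypersensitivity reactions, malignancy, and low white cell, neutrophil and platelet counts. The study stops when two or more subjects have the same event at Grade 3, or "if one subject develops a CTCAE Grade 4 of the following". Neither limb is open-ended.

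The individual stopping rule in Protocol 8.5.1 covers the same seven types (plus bowel events) and is open-ended: "A subject develops a CTCAE Grade 3 or higher of the following".

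Protocol 12.3.1.6.3 gives Grade 4 as "Life-threatening consequences; or urgent intervention indicated" and Grade 5 as "Death related to AE". These are separate grades. For individual terms it defers to the external source: "Please refer to the above-referenced CTCAE document for full description of CTCAE terms".

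**The concern.** A rule that stops the study for one life-threatening event should also stop it for one fatal event of the same kind. As worded, it does so only if the fatal event was at Grade 4 first. On any other fatal course, continuing or stopping is left to the judgement of the Data Monitoring Committee (DMC) and the sponsor.

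This matters most in the 3 mg/kg cohort. Before that cohort opens, escalation is a second barrier: Protocol 6.3 bars it if clinically important safety findings arise at 1 mg/kg, and Protocol 8.8 requires DMC review, a sponsor decision, and that the 8.5.2 criteria have not been met. Once 3 mg/kg dosing is under way no further escalation gate applies. The scheduled DMC review of that cohort comes only when all its subjects have finished treatment (Protocol 8.4 and 10.1).

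**Working it through.** The plan states no figure on this point. The check is a comparison of texts, followed by a count of planned exposure.

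**1. Is the omission consistent with the rest of the protocol?** No. Protocol 8.5.1 uses an open-ended Grade 3 threshold. Protocol 8.4 does the same for ad hoc DMC meetings on disease exacerbations, and so does the last bullet of 8.5.2 for Crohn's exacerbations. Among these graded thresholds, only the automatic study stop lacks the open-ended wording.

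**2. Does another automatic stop cover a death?** None was found in either document. The other automatic bullets of 8.5.2 concern liver enzymes and Hy's Law. The last bullet concerns Crohn's exacerbations and leads to DMC review, not to a stop.

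**3. What does the rule do for one subject with a listed event?** Protocol 12.3.1.6.3 requires each change in severity to be recorded as a new event, so a Grade 4 phase before death counts in its own right.

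| Course in one subject | Current wording | With *Grade 4 or higher* |
|---|---|---|
| Grade 3 only | no stop (needs a second subject) | no stop (needs a second subject) |
| Grade 4 | stop | stop |
| Grade 4, then Grade 5 | stop | stop |
| Grade 3, then Grade 5 | **no stop** | stop |
| Grade 5 directly | **no stop** | stop |

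Only the last two rows change.

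**4. Does the Grade 3 limb need the same edit?** With the one-subject limb amended, any subject at Grade 4 or 5 already stops the study. The two-subject limb then decides only when nobody exceeds Grade 3, and in that case *Grade 3* and *Grade 3 or higher* give the same answer. No edit is needed.

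**5. How much planned exposure could fall outside the automatic stop at 3 mg/kg?**
- Cohort size (Protocol 8.7): 4 CD + 6 UC = 10 subjects, out of 8 + 6 = 14 planned.
- Doses per subject (Protocol synopsis): 4.
- Upper end, event in the first subject before anyone else is dosed: 10 − 1 = 9 other subjects; 9 × 4 = 36 planned doses.
- Lower end, event in the last subject after all others have finished: 0 subjects, 0 doses.

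Replacement subjects are not counted. The range describes exposure before the scheduled DMC review, assuming nobody intervenes.

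**The case against.** The strongest reply is that the gap is nearly empty. A subject dying of anaphylaxis or an opportunistic infection would ordinarily have been in a life-threatening state first, and the severity-change rule in 12.3.1.6.3 would make that a recorded Grade 4 event. What remains is a death with no observed life-threatening phase, such as one between visits that reaches the site only as a death. How many of the seven listed terms can be graded 5 at all cannot be settled from these documents. Both points stand, and they limit the concern without removing it.

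It can also be said that the intent is obvious and that nobody would carry on after a death. "Each investigator will review all available safety data collected at their site on a weekly basis", the medical monitor takes relevant findings to the DMC as needed, and "Adverse events resulting in death must be reported within 24 hours as SAEs". The DMC may change its meeting schedule (8.4), the sponsor may terminate at any time (8.9), and regulators, sites and ethics boards are notified of serious events as Protocol 12.3.1.6.8 sets out. These safeguards are real and make silent continuation unlikely. None is an automatic stop, however: "The sponsor is responsible for the decision to continue, modify or terminate the study". An automatic rule is there so that the outcome does not depend on reading intent into it.

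The 36-dose figure can fairly be criticised as cohort size times doses. It is a bound and should be read only as one.

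**Conclusion.** The concern holds, at low severity. On its literal wording the first bullet of 8.5.2 stops the study for one Grade 4 listed event but not for one Grade 5 listed event without a Grade 4 phase. It is a wording gap in a safety threshold; no deliberate design decision appears to lie behind it.

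The conclusion rests on reading the text literally and on at least one listed term being gradable as 5, which the documents do not show. The exposure range assumes full planned enrolment and dosing at 3 mg/kg; its upper end also assumes that no one acts before the scheduled review, although a discretionary hold after a 24-hour death report is probable. No summary, estimate or sample size is affected.

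**What to change.** In the one-subject limb of the first bullet of Protocol 8.5.2, replace *Grade 4* with *Grade 4 or higher*. Leave the two-subject Grade 3 limb as it is.

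The edit is two words and changes no data collection, sample size or analysis. Protocol 14.6 requires a formal amendment with sponsor, investigator and ethics board approval and regulatory filing, so the sensible course is to include it in the next amendment made for other reasons.

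### Protocol 8.5.2 requires prompt DMC review of severe disease exacerbations for Crohn's disease only; for the 6 UC subjects an event-triggered review is optional

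*Protocol*

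**What the plan says.** Four parts of the protocol bear on what happens after a severe exacerbation of the underlying disease.

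- **8.5.2, Study Stopping Criteria.** The final item reads "Individual reports of exacerbations of Crohn's disease CTCAE Grade 3 or greater, such as" and lists hemorrhage, obstruction, perforation and stenosis at intestinal sites. These reports "will be reviewed by the DMC at the first available date after report" "to determine if modifying the study or stopping the study is recommended". The item does not mention UC.
- **8.4, Data Monitoring Committee.** This section provides for "ad hoc meetings to assess individual exacerbations of CD or UC meeting Common Terminology Criteria for Adverse Events (CTCAE) Grade 3 or greater", with Section 8.5 cited for the definition. The verb is permissive: such meetings may be held. On authority it says: "The sponsor is responsible for the decision to continue, modify or terminate the study".
- **8.3, Safety Data Review.** "The sponsor medical monitor will review all relevant safety findings with the coordinating principal investigator and DMC as needed".
- **8.5.1, Individual Subject Stopping Criteria.** A subject with either disease is stopped if "A subject develops a CTCAE Grade 3 or higher of the following". That list includes the same four bowel events.

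Scheduled DMC meetings (8.4) take place once the whole first cohort has reached Visit 4, and again after the second cohort is complete. SAP 13 gives no trigger for UC and leaves further detail to the DMC charter, which is not among the documents.

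**The concern.** The study is uncontrolled, and Protocol 8.6 describes it as the first in treatment-resistant CD or UC. Safety and tolerability are the primary objective (7.1). Worsening of the underlying bowel disease is therefore one of the signals that the committee most needs to see early.

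The individual rule in 8.5.1 protects the subject who has had the event. The DMC step in 8.5.2 does something else: it obtains independent advice on whether the remaining subjects should go on being dosed. As written, that advice is mandatory after a severe Crohn's exacerbation and discretionary after a severe UC exacerbation. No reason is given for the difference. UC subjects also enter directly at the higher dose.

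Section 8.4 sends the reader to 8.5 for a definition covering both diseases, and 8.5 has no UC exacerbation item. This looks like an update left incomplete when UC was added, and not a deliberate choice.

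**Working it through.** **Step 1: planned numbers** (Protocol synopsis and 8.7). Crohn's disease (CD) at 1 mg/kg: 4. CD at 3 mg/kg: 4. UC at 3 mg/kg: 6.

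- Total: 4 + 4 + 6 = 14, which reproduces the stated total.
- At 3 mg/kg: 4 + 6 = 10.
- UC share overall: 6/14 = 42.9%.
- UC share at 3 mg/kg: 6/10 = 60.0%.

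**Step 2: routes to the DMC after a Grade 3 or greater exacerbation.**

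| Route | CD subject | UC subject |
|---|---|---|
| 8.5.2, exacerbation item | Required, at the earliest date available | Not named |
| 8.4, ad hoc meeting | Optional | Optional |
| 8.3, via the medical monitor | Discretionary | Discretionary |

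Only the first row creates an obligation, and it covers CD only. The other 8.5.2 rules (the Grade 3/4 event list, liver toxicity, Hy's Law) apply to both diseases, but none of them names a disease exacerbation or any of the four bowel events.

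**Step 3: could the scheduled meetings fill the gap?** The first uses data from the 1 mg/kg cohort, which is CD only, and UC subjects enroll after escalation (8.1). So it cannot contain UC data. The second follows completion of the second cohort. Protocol 10.1 places that review after all of the cohort's subjects have finished the treatment period and its assessments. The last dose is on Day 42, so dosing is over by then. SAP 13 words the timing more loosely, as after enrollment in each cohort. Even on that reading the meeting is tied to a milestone and not to an event.

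**Step 4: could the situation arise?** The documents give no exacerbation rate. As an illustration only, assume a per-subject risk p and independent subjects. The chance of at least one Grade 3 or greater exacerbation among 6 UC subjects is 1 − (1 − p)^6:

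| Assumed p | Chance of at least one in 6 |
|---|---|
| 5% | 26.5% |
| 10% | 46.9% |
| 20% | 73.8% |
| 30% | 88.2% |

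At any of these risks the case is realistic enough for the rule to provide for it.

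**Step 5: after the change.** Required event-triggered review would cover 14 of 14 subjects instead of 8 of 14 (57.1%), and 10 of 10 at 3 mg/kg instead of 4 of 10 (40.0%).

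**The case against.** The strongest reply is that the practical consequence is small. A UC subject with any of the four bowel events at Grade 3 or higher is stopped under 8.5.1. Sites review safety data weekly and report concerns to the medical monitor (8.3). Serious adverse events reach the sponsor and the CRO within 24 hours (12.3.1.6.6.1). The sponsor may end the study whenever it chooses (8.9). The DMC can adjust its own meeting schedule, and 8.4 shows that the authors had UC in mind. The charter may already contain a UC rule.

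All of that stands, and it limits the point. It does not remove it. Each of these steps either protects only the affected subject, runs through the sponsor, or is optional. The charter's content is unknown, and the protocol states the rule itself for CD.

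Four stronger readings are tempting, and the documents do not support them.

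- *A reader might infer that UC subjects are outside required DMC review altogether.* They are not: 8.4 requires review after the second cohort, which includes them. What is missing is timely, event-triggered review.
- *A reader might compare the 11 events in 8.5.1 with 8.5.2 and conclude that only the four bowel events in UC lack a required study-level response.* For the other seven, 8.5.2 needs the same Grade 3 event in two subjects or a single Grade 4. One Grade 3 event of those seven in one subject requires no study-level action in either disease, so a simple count of events misstates the contrast.
- *A reader might contrast a Grade 4 perforation in UC, which does not stop the study, with a Grade 4 injection site reaction, which does.* A Grade 4 perforation in CD does not stop the study automatically either; as an exacerbation it goes to the DMC for a recommendation. The contrast is not specific to UC.
- *A reader might treat "CD exacerbation" in the 8.3 attention list as a second omission.* That entry is under reactions seen with other biologics. Adding UC would assert something about other drugs that the documents do not show.

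**Conclusion.** The point holds as an inconsistency between 8.4 and 8.5.2 in an operative safety rule. Following 8.5.2 as written, 6 of 14 planned subjects (42.9%), and 6 of 10 at 3 mg/kg (60.0%), have no required event-triggered DMC review of a Grade 3 or greater exacerbation. Their only scheduled DMC review comes after dosing has ended.

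This rests on three things: a literal reading of 8.5.2; planned numbers, since the total is approximate and subjects who withdraw before the third dose may be replaced; and a charter that has not been seen. Confidence is high for the wording gap and lower for its practical effect, because a conscientious sponsor and committee could well convene under the optional provisions. The change is worth making, but this is not a finding that UC subjects are unprotected.

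**What to change.** In the final item of Protocol 8.5.2, insert *or ulcerative colitis* directly after the reference to Crohn's disease, so that the required review covers Grade 3 or greater exacerbations of both. The text of 8.4 can stay: its pointer to 8.5 then leads to a definition that includes UC, and the obligation sits in 8.5.2. Leave the attention list in 8.3 as it is. Check that the DMC charter carries the same trigger, and amend it if not.

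The cost is three words in the protocol, a charter check and, at most, an occasional extra ad hoc DMC review. Sample size and analyses do not change. The DMC still recommends and the sponsor still decides.
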